**Not assessable**

The causal relationship between the study drug and the AE cannot be judged.

**hh. Adverse events reporting procedures**

A special section is designated to adverse events in the case report form. For each subject, adverse events occurring after signing the informed consent must be recorded on the applicable adverse events page(s) in the case report form. Recording should be done in a concise manner using standard, acceptable medical terms. The adverse event recorded should not be a procedure or a clinical measurement (i.e., a laboratory value or vital sign) but should reflect the reason for the procedure or the diagnosis based on the abnormal measurement. If, in the investigator's judgment, a clinically significant worsening from baseline is observed in laboratory or other parameters, physical exam finding, or vital sign, a corresponding clinical adverse event should be recorded on the adverse event page(s) of the CRF. If a specific medical diagnosis has been made that diagnosis should be recorded on the adverse event page(s) of the CRF.

SARS-CoV-2 VAC3 study

EudraCT 2021-002348-57

Version 4.0, 10. August 2021

SAEs and any newly identified pregnancy (maternal or paternal exposure), malignancy, overdose, opportunistic infection or case of active TB occurring after first administration of study agent in subjects participating in this clinical trial requires submission of a Safety Report Form to the Sponsor (only if other sites are reporting SAE) within 24 hours of notification or observation.

*The following details must thereby be entered:*

- Type of adverse event
- Start (date and time)
- End (date and time)
- Severity (mild, moderate, severe)
- Serious (no / yes)
- Unexpected (no / yes)
- Outcome (resolved, ongoing, ongoing – improved, ongoing – worsening)
- Relation to study drug (unrelated, possibly related, definitely related)

Adverse events are to be documented in the case report form in accordance with the above mentioned criteria.

ii. Reporting procedures for SAEs

In the event of serious, the investigator has to use all supportive measures for best patient treatment. A serious adverse event must be reported if it occurs during a subject's participation in the study (whether receiving study agent or not) or within six (6) months of receiving the last dose of study agent.

A Safety Report Form must be completed and faxed to the Sponsor ([name]) 24 hours of observation or notification of the event. The sponsor will be responsible for potential SUSAR assessment (see below) and reporting SAEs including potential SUSAR to the manufacturing company. A written report is also to be prepared and made available to the clinical investigator within five days.

The following details should at least be available:

- Patient initials and number
- Patient: date of birth, sex, ethical origin

SARS-CoV-2 VAC3 study

EudraCT 2021-002348-57

Version 4.0, 10. August 2021

- The suspected investigational medical product (IMP)
- The adverse event assessed as serious
- Short description of the event and outcome

Any serious adverse event that is ongoing when a subject completes his/her participation in the trial must be followed until any of the following occurs:

- The event resolves or stabilizes
- The event returns to baseline condition or value (if a baseline value is available)
- The event can be attributed to agent(s) other than the study agent, or to factors unrelated to study conduct

jj. Reporting procedures for SUSARs

All SAEs will be evaluated regarding a possible classification as SUSAR by the sponsor, who will then perform all necessary reports to the manufacturing/distributing pharmaceutical company and forward the SUSAR to the CRO. The CRO will be responsible for reporting SUSARs to the regulatory authorities. In addition, due to their possible safety concern for the study participants, all SUSARs need to be reported to the Institutional Review Board / Independent Ethics Committee (IRB / IEC).

These reports are time critical and should be done within a maximum of 7 days (fatal or life threatening outcome) or 15 days (non fatal, not life threatening). The representative of the Sponsor Investigator shall inform all investigators concerned of relevant information about Serious Unexpected Suspected Adverse Reactions that could adversely affect the safety of subjects.

Such reports shall be made by the study management and the following details should be at least available:

- Patient inclusion number
- Patient: year of birth, sex, ethical origin
- Name of investigator and investigating site
- Period of administration
- The suspected investigational medical product (IMP)
- The adverse event assessed as serious and unexpected, and for which there is a reasonable suspected causal relationship to the IMP

SARS-CoV-2 VAC3 study

EudraCT 2021-002348-57

Version 4.0, 10. August 2021

- Concomitant disease and medication
- Short description of the event:
  - Description
  - Onset and if applicable, end
  - Therapeutic intervention
  - Causal relationship
  - Hospitalization or prolongation of hospitalization

SARS-CoV-2 VAC3 study

EudraCT 2021-002348-57

Version 4.0, 10. August 2021

## 10. METHODOLOGY

### 7.1 Study design and blood samples

A randomized controlled single-blind phase II trial will be performed. A total of 68 patients with current rituximab therapy who did not develop humoral immune response to SARS-CoV-2 after vaccination with mRNA SARS-CoV-2 vaccine (Biontech/Pfizer or Moderna). Four study visits per patient will be planned during the course of the trial: screening visit (-0-14 days), baseline, week 1, week 4. Patients will be unblinded at week 4. In addition, patients who did not show humoral response at week 4 will be invited for two additional study visits at week 8 and week 12 in an open label approach. Vaccination will take place at baseline visit.

Blood samples for the determination of SARS-CoV-2 antibodies will be obtained at screening visit, at week 1, week 4 and during the potential extension of the study at week 8 and week 12.

### 7.2 Study procedures

#### 7.2.1 General rules for trial procedures

- All study measures like blood sampling and measurements have to be documented with the date (dd:mm:yyyy).
- In case several study procedures are scheduled simultaneously, there is no specific sequence that should be followed.
- The dates of all procedures should be according to the protocol. The time margins mentioned in the study flow chart are admissible. If for any reason, a study procedure is not performed within scheduled margins, a protocol deviation should be noted, and the procedure should be performed as soon as possible or as adequate.
- If it is necessary for organizational reasons, it is admissible to perform procedures scheduled for one visit at two different time points. Allowed time margins should thereby not be exceeded.

SARS-CoV-2 VAC3 study

EudraCT 2021-002348-57

Version 4.0, 10. August 2021

## 7.2.2 Study visits

### 7.2.2.1 Screening visit (visit 1, -1-28 days, at least 4 weeks after the second immunization with mRNA SARS-CoV-2 vaccine)

The investigator will inform the subject about the procedures, risks, and benefits of the study. Participants will be informed about future visits, which will be synchronized with the appointment for the third vaccination.

Fully informed, written consent must be obtained from each subject before any assessment is performed. The subject must be allowed sufficient time to consider his/her participation in the study.

The following assessments will be performed:

- Inclusion and exclusion criteria
- Demographic data, including sex, age, weight, and height
- Medical history and concomitant medication
- Assessment of adverse reactions after the mRNA SARS-CoV-2 vaccination
- Assessment of recent COVID-19 disease
- Blood will be drawn:
  - 16 ml of blood will be drawn for PBMC isolation and determination of cellular immunity
  - 8 ml of blood will be drawn for SARS-Cov-2 antibody level detection (prior vaccination).
  - 8 ml of blood will be drawn for determination of leukocyte subpopulations
  - 8 ml of blood will be drawn for biobanking of serum
  - 20 ml of blood will be drawn for routine laboratory testing: blood count, chemistry, coagulation factors
- Pregnancy test in women with childbearing potential
  - Randomization to one of the three vaccines: mRNA SARS-CoV-2 (Biontech/Pfizer or Moderna) or vector SARS-CoV-2 vaccination (AstraZeneca)
- SARS-CoV-2 vaccine appointment

### 7.2.2.2. Baseline visit (visit 2, week 0, max. 28 days after visit 1)

[116]

SARS-CoV-2 VAC3 study

EudraCT 2021-002348-57

Version 4.0, 10. August 2021

The following activities will be performed:

- The investigator will ask all subjects about any adverse experiences occurring since Visit 1 (screening). All adverse experiences will be documented in the CRF.
- Patients will receive a patients diary, fever thermometer and spacer
- Application of mRNA SARS-CoV-2 (Biontech/Pfizer or Moderna) or vector SARS-CoV-2 vaccine (AstraZeneca)
- Patients health status will be observed for additional 30 minutes by a clinician and a nurse in case of any acute reactions to the vaccination

#### **7.2.2.3. Visit 3 (1 week after the third SARS-CoV-2 vaccination)**

The following activities will be performed:

- The investigator will ask all subjects about any adverse experiences occurring since Visit 2. All adverse experiences will be documented in the CRF.
- Patient´s diaries will be discussed
- Blood will be drawn:
  - 16 ml of blood will be drawn for PBMC isolation and determination of cellular immunity
  - 8 ml of blood will be drawn for SARS-Cov-2 antibody level detection
  - 6 ml of blood will be drawn for determination of leukocyte subpopulations
  - 8 ml of blood will be drawn for biobanking of serum
  - 20 ml of blood will be drawn for routine laboratory testing: blood account, chemistry as well as thrombocytes and coagulation factors
  - 8 ml blood will be drawn for detection of anti-PDE4D antibody

#### **7.2.2. 4. Visit 4 (4 weeks after the third SARS-CoV-2 vaccination)**

The following activities will be performed:

- The investigator will ask all subjects about any adverse experiences occurring since Visit 3. All adverse experiences will be documented in the CRF.
- Patient´s diary will be returned to investigator
- Blood draw:
  - 8 ml of blood will be drawn for SARS-Cov-2 antibody level detection

SARS-CoV-2 VAC3 study

EudraCT 2021-002348-57

Version 4.0, 10. August 2021

- 6 ml of blood will be drawn for determination of leukocyte subpopulations
- 8 ml of blood will be drawn for biobanking of serum
- 20 ml of blood will be drawn for routine laboratory testing: blood account, chemistry, coagulation factors
- 8 ml blood will be drawn for detection of anti-PDE4D antibody

#### **7.2.2.5. Visits 5 (week 8) and 6 (week 12) (only for patients enrolling in open label extension)**

Fully informed, written consent to the extension period must be obtained from each subject before any assessment is performed. The subject must be allowed sufficient time to consider his/her participation in the open label extension.

The following activities will be performed:

- The investigator will ask all subjects about any adverse experiences occurring since Visit 3. All adverse experiences will be documented in the CRF.
- Blood draw:
  - 8 ml of blood will be drawn for SARS-CoV-2 antibody level detection
  - 8 ml of blood will be drawn for biobanking of serum

### **7.2.3 Determination of the humoral and cellular immunity**

#### **7.2.3.1 Determination of serum antibodies against vaccination antigens**

Analysis will be performed at the Department of Laboratory Medicine, Medical University of Vienna. All procedures will be carried out according to standard operating procedures in an ISO 9001:2015 certified environment (ref: 10.1089/bio.2018.0032).

Previous SARS-CoV-2 infection will be detected using nucleocapsid-based chemiluminescence assays (e.g., Roche SARS-CoV-2 NC total antibody ECLIA, Abbott SARS-CoV-2 NC IgG CMIA). Vaccination response will be assessed by spike-protein-based assays (e.g., Technozym RBD ELISA, Siemens RBD immunoassay, Roche SARS-CoV-2 RBD ECLIA).

All analyses will be carried out at the Department of Laboratory Medicine, Medical University of Vienna.

Neutralization assays will be performed as described earlier.

SARS-CoV-2 VAC3 study

EudraCT 2021-002348-57

Version 4.0, 10. August 2021

### **7.2.3.2 Determination of cellular immune response**

To investigate cellular immunity following SARS-CoV-2 vaccination Peripheral blood mononuclear cells (PBMCs) will be isolated from heparinized venous blood by density gradient centrifugation at 400 *g* of heparinized blood over LSM 1077 Lymphocyte Separation Medium, cryopreserved and stored in liquid nitrogen for later use.

## **7.3 Study endpoints**

### **7.3.1 Primary study endpoint**

Difference in SARS-CoV-2 antibody seroconversion rate by week 4 after vaccination boost at baseline between 3rd mRNA SARS-CoV-2 (Biontech/Pfizer or Moderna) and vector SARS-CoV-2 vaccine (AstraZeneca).

### **7.3.2 Secondary study endpoints**

The secondary endpoints of this study are:

- Overall SARS-Cov-2 antibody seroconversion rate by week 4 after vaccination boost at baseline
- Difference in overall SARS-Cov-2 antibody seroconversion rate by week 4 after vaccination boost at baseline between patient with and without B-cell repopulation.
- Antibody concentrations of SARS-CoV-2 ELISA 4 weeks after vaccination boost at baseline.
- Effect of immunosuppressive comedication on SARS-Cov-2 antibody seroconversion rate by week 4 after vaccination boost at baseline
- Evaluation of cellular immunity before and one week after the vaccination.
- Safety of vaccination boost.

SARS-CoV-2 VAC3 study

EudraCT 2021-002348-57

Version 4.0, 10. August 2021

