vaccinated persons had lower peak viral load and shorter duration of RT-PCR-positive results for SARS-CoV-2 compared to controls, suggesting that the vaccine is effective in reducing transmission.

Patients with immunosuppression with COVID-19 may be at higher risk of hospitalization and ICU admission than matched comparators. An mRNA vaccine vaccination should be performed as primary immunization with two vaccine-doses 21 or 28 days apart. There are no data about the efficacy and safety of mRNA vaccine against SARS-CoV-2 in patients with a chronic immune-mediated disease such as rheumatoid arthritis, certain kinds of vasculitis, lupus multiple sclerosis. However, after vaccination, immune responses might vary among immunosuppressed patients, dependent upon underlying clinical conditions and the level of immunosuppression. Moreover, it is not clear whether mRNA vaccination against SARS-CoV-2 in the immunosuppressed has a protective effect at all. Specifically, B-cell depleting therapies like CD20 antagonists rituximab have a high risk of vaccination failure. As for other vaccines, the efficacy of a COVID-19 vaccine may be reduced in patients treated with rituximab. For patients treated with rituximab, it is preferable to administer the vaccine at least 6 months after the last infusion to have the highest possible number of restored B-cells. The current treatment scheme for rituximab is 500mg or 1000mg intravenously every 6 months.

However, the vaccine is not contraindicated in this population and the treating physician should discuss with the patient the appropriate timing of vaccination taking into consideration the context of pandemic, the risk of poor COVID-19 disease prognosis, and a possibly reduced humoral response to vaccination under rituximab treatment.

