### 6.5. Randomization Procedure

SARS-CoV-2 VAC3 study

EudraCT 2021-002348-57

Version 4.0, 10. August 2021

The web-based computerized randomization algorithm “Randomizer for Clinical Trials” by the Medical University of Vienna will be used for randomization. Patients will be randomized in a 1:1 ratio between the third dose mRNA SARS-CoV-2 boost (Biontech/Pfizer or Moderna, respective of their initial vaccination compound) and a single dose boost vector SARS-CoV-2 vaccine (AstraZeneca). Randomization will be stratified by presence or absence of B-cell depletion (determined at screening visit).

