## 9. STATISTICAL ANALYSIS

### 9.1 Sample size considerations

According to the available number of patients at our Department, including estimates of non-responders to a standard protocol of mRNA vaccination, and expected participation rates, we will attempt to include 68 patients into this trial. Based on a Chi test comparing 3rd mRNA versus vector vaccine, this number of patients will allow to achieve at least 80% power at a minimal detectable difference of 28% (5% of responders in the mRNA vaccine group versus 33% of responders in the vector vaccine group).

For differences smaller than the minimum detectable difference statistical significance will not be possible to claim.

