### 9.3 Endpoints analysis

[124]

SARS-CoV-2 VAC3 study

EudraCT 2021-002348-57

Version 4.0, 10. August 2021

The primary endpoint (difference in SARS-CoV-2 antibody seroconversion rate by week 4 after vaccination boost at baseline between third mRNA SARS-CoV-2 (Biontech/Pfizer or Moderna) and vector SARS-CoV-2 vaccine (AstraZeneca)) will be analyzed using Chi-squared Test. For the seroconversion rates, 95% confidence intervals will be calculated. All subjects with available antibody responses fulfilling the eligibility criteria will be included in the analysis.

The secondary endpoints (see section 7.3.2) will be analyzed using descriptive statistics.

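### Randomisation is stratified by B-cell depletion, but no planned analysis estimates the vaccine difference within either stratum, so an effect confined to patients with B cells could be diluted unseen

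*Supplement*

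**What the plan says.** All references are to protocol Version 4.0, whose section 9 is the analysis plan.

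- **Section 6.5** allocates patients 1:1 and names one stratification factor: "Randomization will be stratified by presence or absence of B-cell depletion (determined at screening visit".
- **Sections 7.3.1 and 9.3** define the primary endpoint as the difference in week-4 seroconversion rate between the two vaccines and analyse it by a chi-squared test. No stratum or B-cell term is named.
- **Section 7.3.2** has one endpoint that uses B-cell status: "Difference in overall SARS-Cov-2 antibody seroconversion rate by week 4 after vaccination boost at baseline between patient with and without B-cell repopulation". The first endpoint in that list uses the same word, overall, for the whole-trial rate, so here too both vaccines are taken together.
- **Section 9.3** adds "The secondary endpoints (see section 7.3.2) will be analyzed using descriptive statistics". That covers only what section 7.3.2 lists.
- **Section 3** says it is preferable to vaccinate at least six months after the last rituximab infusion, "to have the highest possible number of restored B-cells".

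No section plans a vaccine comparison within a B-cell group, a stratified test or a comparison of effects between B-cell groups.

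**The concern.** B-cell status is not an arbitrary subgroup here. It is the only factor used to stratify randomisation, and the protocol's own background treats restored B cells as favourable for response. It is therefore plausible, though nowhere stated, that depleted patients respond to neither vaccine and that any difference between vaccines lies among patients who have B cells.

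In that case the overall difference is the effect in patients with B cells multiplied by their share of the sample, and the protocol does not fix that share. A modest, non-significant overall difference could then mean either that the vaccines are equivalent or that one is better in part of the population. Equally, an overall winner might do nothing in depleted patients. The pooled B-cell endpoint shows whether B cells predict seroconversion. It cannot show which vaccine works in whom.

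**Working it through.** **Inputs.**
- 34 per arm, from "we will attempt to include 68 patients into this trial" with 1:1 allocation.
- Planning rates in section 9.1: "5% of responders in the mRNA vaccine group versus 33% of responders in the vector vaccine group".
- Two-sided alpha of 0.05. This is not stated; it is assumed from the non-directional alternative hypothesis in section 5.1 and from "For the seroconversion rates, 95% confidence intervals will be calculated".
- Share f of patients with B cells: not in the documents; 30%, 50% and 70% are assumed.
- Response in depleted patients: not in the documents; 5% in both arms or 0% in both arms is assumed.

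**Formula** (normal approximation, no continuity correction):

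power = Φ[(d − 1.96·se0)/se1], with d = p2 − p1, se0 = √(2·p̄(1−p̄)/n) and se1 = √((p1(1−p1) + p2(1−p2))/n).

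**Step 1: the plan's own figure.** With p1 = 0.05, p2 = 0.33 and n = 34, p̄ = 0.19, se0 = √(2 × 0.1539/34) = 0.0951 and se1 = √(0.2686/34) = 0.0889. Then (0.28 − 1.96 × 0.0951)/0.0889 = 1.05, so power is 85%. Exact enumeration of the Pearson test gives 89%. The claim in section 9.1 of at least 80% power holds.

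**Step 2: the same effect confined to patients with B cells.** The overall rate in each arm is f × (rate with B cells) + (1−f) × (rate in depleted), so the overall difference is 28 × f points. For f = 50% and 5% in depleted patients, the rates are 5% and 19% and p̄ = 0.12. Then se0 = 0.0788, se1 = 0.0770, and (0.14 − 1.96 × 0.0788)/0.0770 = −0.19, so power is 43%.

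| Share with B cells | Overall difference | Rates and power, depleted 5% | Rates and power, depleted 0% |
|---|---|---|---|
| 30% | 8.4 points | 5.0% vs 13.4%: 22% | 1.5% vs 9.9%: 32% |
| 50% | 14.0 points | 5.0% vs 19.0%: 43% | 2.5% vs 16.5%: 50% |
| 70% | 19.6 points | 5.0% vs 24.6%: 63% | 3.5% vs 23.1%: 67% |

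Exact Pearson power is 24% and 30%, 46% and 57%, and 68% and 74% in the three rows, so the picture does not depend on the approximation.

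**Step 3: what a stratum estimate would deliver.** In the stratum with B cells, the half-width of the 95% interval is about 1.96·√(0.2686/m) with m patients per arm.

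| Share | m per arm | Half-width | Power within stratum |
|---|---|---|---|
| 30% | 10 | 32 points | 35% |
| 50% | 17 | 25 points | 55% |
| 70% | 24 | 21 points | 71% |

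If the rates were 20% and 60% instead, the half-width at 17 per arm would be 1.96·√((0.16 + 0.24)/17) = 30 points. For the difference between stratum effects at f = 50%, the standard error is √(0.2686/17 + 2 × 0.0475/17) = 0.146. Power is Φ(0.28/0.146 − 1.96), about 48%; over the three shares it runs from roughly 36% to 50%. All these figures are rough in strata this small.

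**Step 4: what a stratified primary test would deliver.** This depends on the rates. With assumed rates of 2% in depleted patients and 20% versus 60% in the others, at 17 per arm in each stratum, exact power is 56% for the pooled test, 66% for Cochran-Mantel-Haenszel and 70% within the stratum with B cells. With the planning rates at f = 50% and no response in depleted patients, exact power is already 57% overall against 58% within the stratum, so there is almost nothing to recover.

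**The case against.** The strongest reply is that the quoted endpoint contains no error. It asks whether B-cell status predicts seroconversion, and pooling the vaccines is right for that question. A reader might infer that this endpoint causes the dilution. It does not: any dilution arises in the unstratified primary comparison of sections 7.3.1 and 9.3, and the secondary endpoint merely fails to reveal it. This part of the objection stands.

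A reader might also infer that the trial is bound to report a tie. The documents do not support that. They give no share of patients with B cells, no response rates by stratum, and nothing to show that the difference between vaccines varies with B-cell status. At a 70% share, power is still 63–67%. A larger confined effect, 5% versus 61% at a 50% share, averages 0.5 × 56 = 28 points and keeps the planned power. Constructed examples are fragile too. Results of 3/17 versus 10/17 with B cells and 1/17 versus 0/17 in depleted patients pool to 4/34 versus 10/34 (p = 0.072), but without the single depleted responder 3/34 versus 10/34 gives p = 0.031.

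Nor may one conclude that a stratified primary test would be useless. On that first example, Cochran-Mantel-Haenszel gives 3.0²/2.318 = 3.88, p = 0.049. It does not, however, display the effect in each stratum.

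Finally, the stated question concerns rituximab-treated non-responders as one group, every overall risk difference depends on case mix, and a stratum table could be produced without being planned. All true. But a table outside section 7.3.2 would be post hoc, and this factor is the one the design itself singled out.

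**Conclusion.** The concern holds as an omission. Version 4.0 stratifies randomisation by B-cell depletion, ignores the stratum in the primary test, and pools the vaccines in its only B-cell endpoint, so the vaccine difference is not estimated in either stratum. The primary test remains a valid answer to the overall question.

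The possible consequence is conditional. If the planning effect exists only in patients with B cells, overall power falls from about 85% to roughly 22–32%, 43–50% or 63–67% at shares of 30%, 50% or 70%, and no planned output would show why. These figures rest on assumed shares, assumed response of 5% or 0% in depleted patients, and an assumed two-sided alpha of 0.05. They show what can happen, not what will. The gain from the remedy is mainly a reported estimate with its uncertainty; the gain in power ranges from negligible to moderate.

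**What to change.** In sections 7.3.2 and 9.3, add:

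1. Seroconversion by vaccine within each randomisation stratum (B-cell depletion present or absent, as recorded at screening for randomisation), with the vaccine difference and its 95% Newcombe or Miettinen-Nurminen interval.
2. The difference between the two stratum effects with a 95% confidence interval.
3. A statement that both are secondary and descriptive, with no claim of significance.
4. Analysis of the primary endpoint stratified by the randomisation factor, for example by Cochran-Mantel-Haenszel. This can recover some power but does not replace items 1 and 2, because it returns one common effect.

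Tying the table to the stratum recorded at screening also avoids an ambiguity: the documents give no cut-off or time point linking repopulation in section 7.3.2 to depletion in section 6.5.

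The cost is one table and a few sentences. B-cell status and week-4 antibodies are already collected. The downside is width, about ±25 to 30 points at 17 per arm, so the table must be read as an aid to interpreting the overall result and not as confirmation of a subgroup effect.
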